7.4 Treatment of HF

7.4.1 HF treatment by visit

For the Enrolled Set, pharmacological treatment of HF will be analysed at Visit 1, additionally stratified by inclusion into the prospective period of the study.

For the Follow-up Set, pharmacological treatment of HF will be analysed additionally at Visit 2 and Visit 3.

HF treatment at Visit X is any treatment of HF with start date prior to Visit X or at Visit X and ongoing at Visit X.

Dose and frequency of HF medication will be concatenated for use of analysis (e.g. dose: “10 mg”, frequency: “OD”, combined value: “10 mg – OD”). In case, dose unit is “other”, the respective specified dose unit will be used.

The duration of specific HF medication at Visit 1 will be evaluated in groups (≤ 1 year, > 1 year to ≤ 2 years, > 2 year to ≤ 3 years, > 3 years) by preferred name; it will be derived from the calculated duration of treatment via $(date\ of\ V1 - start\ date)/365.25$ or (in case of missing or incomplete start date) using the approximate start time of medication (1 year ago, 2 years ago, 3 years ago, > 3 years ago). In case of incomplete start date and missing approximate start time, the start date will be imputed using the methods for handling of missing values ([Section 7.10](#)). If multiple HF medications with the same code are documented for the same patient at Visit 1, the longest duration of treatment will be used for analysis.

The following analyses will be provided:

- Incidence rates for HF treatments by ATC level 2 and preferred name. For this analysis, the ATC level 2 “Diuretics” (C03) will be split up into “Diuretics – without Mineral Corticoid Antagonists” and “Diuretics – Mineral Corticoid Antagonists”. Mineral Corticoid Antagonists are any medications with ATC code C03DA.

- Incidence rates for HF treatments by preferred name and concatenated dose and frequency.
- Incidence rates for HF treatments by preferred name and duration of HF treatment (only Visit 1).

7.4.2 Adherence to ESC guidelines (primary analysis)

For each patient, HF treatment at every visit will be classified with respect to adherence to ESC guidelines on level 1 and level 2 as outlined in [Section 4.5.1](#). Respective frequency distributions of adherence (yes, no) will be provided for the Follow-up Set for every visit.

The primary analysis will be performed on guideline adherence level 1 (as described in [Section 4.5.1](#)) as follows: based on the patients in the Follow-up Set treated not according to ESC guidelines at Visit 1, absolute and relative frequencies of A2 will be provided. The proportions within this analysis will be calculated twice, with and without considering missing values for A2. 95%-CIs will be provided for the proportions.

This analysis of A2 will be repeated for all patients in the Follow-up Set treated according to guidelines (level 1) at Visit 1.

For sensitivity, the analyses of A2 conditional to guideline adherence at Visit 1 will be repeated for guideline adherence level 2 (drug type and dose).

For the Enrolled Set, adherence to ESC guidelines (level 1 and level 2) will be analysed at Visit 1, additionally stratified by inclusion into the prospective period of the study.

In addition, the analyses of guideline adherence with respect to drug type will be repeated without taking into account the indication of the applied medications. This means, patients taking an ACEi, ARB, Beta-Blocker or MRA without HF indication will not automatically be classified as non-adherent in this analysis. Instead, these drugs will be included in the analysis and can contribute to a guideline adherent treatment of the patient.

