2.1 Primary objective(s)

To assess if NT-proBNP measurement-guided cardiologist-referral of CHF patients, who are currently judged by their primary care physician as being clinically stable*, leads to optimization of HF treatment, defined as adherence[#] to level I-A treatment recommendations of the current[§] ESC guidelines for the treatment of HF.

***Note:** Within this study, clinically stable patients are defined as those patients, who by the judgement of their primary care physician currently do not require and, in the last 3 months prior to the baseline visit have not had, any change in their pharmacological or device treatment of HF.

[figure not shown]
#Note: Adherence to the recommendations of the ESC guidelines within this study is defined as the prescription of all HF specific drugs with level I-A recommendation for a given patient's clinical status at a dose $> 50\%$ of the recommended daily dose.

§Note: Current ESC guidelines are those which are in force on the date the patient signs the informed consent form.

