2.4 Objectives and related endpoints

Table 2-1 Objectives and related endpoints

OBJECTIVE	Endpoint Title, Description and Reporting Time Frame for analysis and Unit of Measure	Stat Analysis Section
Primary		
To assess if NT-proBNP measurement-guided cardiologist-referral of CHF patients, who are currently judged by their primary care physician as being clinically stable, leads to optimization of HF treatment, defined as adherence to level I-A treatment recommendations of the current ESC guidelines for the treatment of HF.	Title: Change of the proportion of clinically stable patients whose therapy regimen adheres to ESC guideline recommendations before and after specialist referral. Description: Assessment of patients' treatment regimen with respect to ESC guideline adherence at baseline (Visit 1) and after referral to a specialist (visit 2); the change between both visits will be calculated to reflect the proportion of patients for whom optimization was deemed necessary and implemented. For definitions of clinically stable patients and adherence to current ESC guidelines see Section 2.1 . Units of Measure: Bivariate absolute and relative frequency distributions including 95%-confidence intervals. Time Frame: Baseline, Visit 2	Section 9.4

OBJECTIVE	Endpoint Title, Description and Reporting Time Frame for analysis and Unit of Measure	Stat Analysis Section
Secondary		

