9.4.4 Sensitivity analyses

In order to detect possible country effects or effects of further subgroups and allow for a site and patient profiling, stratified analyses of the primary endpoint will be performed at least for the following subgroups:

- Country/region cluster information for site
- Sex
- Age groups
- NT-proBNP levels

Please refer for details to the Statistical Analysis Plan.

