9.8 Sample size calculation

The study is powered to estimate the proportion of patients switching from a non-ESC guideline recommendations-adherent treatment to regimen adhering to these recommendations after referral to a cardiologist based on all patients who at baseline are judged by their primary care physician to be clinically stable and show NT-proBNP levels ≥ 600 pg/ml.

Based on the data from Dahlstrom et al ([Dahlstrom, Hakansson et al. 2009](#)), showing that only 20% of patients followed by primary care physician receive both Renin-Angiotensin System inhibitors and beta-blockers at a dose $\geq 50\%$ of the recommended, we conservatively assume 20% as the percentage of CHF patients that will be treated in accordance to the ESC guidelines (i.e. prescription of any drugs with level I-A recommendation for a given patient's

clinical status at a dose of > 50% of the recommended daily dose) at baseline (Visit 1). In addition, we assume that after referral to a specialist (Visit 2), the proportion will increase to 30% ([Maggioni, Anker et al. 2013](#)). Although there are no data in the literature measuring the clinical impact of increasing guideline-adherence of treatment in HF, it has been clearly demonstrated that a 10% increase in acute coronary syndrome is clinically highly significant. In fact, for every 10% increase in guideline-adherence at a hospital center, the in-patient's mortality odds ratio falls by a corresponding 39%. Similarly, for every 10% increase in appropriate dosing, the patient's mortality odds ratio falls by a corresponding 18% ([Mehta, Chen et al. 2015](#)).

We further assume that around 25% of patients without ESC guideline recommendations-adherent treatment at baseline (i.e. prior to referral to a cardiologist) will receive optimization (i.e. ESC guideline adherent treatment) of their HF treatment post referral to the cardiologist. This proportion can be estimated with a precision of $\pm 2\%$ using a 95%-CI by including 1,728 patients into the analysis; for subgroup analyses (e.g. on country level) the range of a 95%-CI increases, however it is still possible to estimate the proportion with a precision of $\pm 5\%$ for subgroups of 300 patients.

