3.1 Primary objective(s)

The primary objective of this study is to assess if NT-proBNP measurement-guided cardiologist-referral of chronic heart failure (CHF) patients, who are currently judged by their primary care physician as being clinically stable^{*}, leads to optimization of HF treatment, defined as adherence[#] to level I-A treatment recommendations of the current[§] ESC guidelines for the treatment of HF.

***Note:** Within this study, clinically stable patients are defined as those patients, who by the judgement of their primary care physician currently do not require and, in the last 3 months prior to the Baseline visit have not had, any change in their pharmacological or device treatment of HF.

#Note: Adherence to the recommendations of the ESC guidelines within this study is defined as the prescription of all HF specific drugs with level I-A recommendation for a given patient's clinical status at a dose > 50% of the recommended daily dose.

§Note: Current ESC guidelines are those which are in force on the date the patient signs the informed consent form.

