4.5 Measures

4.5.1 Primary measures

The primary effectiveness measure is the adherence (yes/no) of HF treatment to the current ESC guideline^{1, 2}. The following measures of HF therapy and concomitant medication will be used for derivation of the primary effectiveness measure:

- Active ingredient

- Single dose and dose unit
- Start and end date

Following the ESC guideline definitions, two levels of guideline adherence will be used for the analysis: adherence with respect to drug types (level 1) and adherence with respect to drug types **and** drug dose (level 2). The exact definitions of both levels of guideline adherence are provided in [Table 4-2](#).

Table 4-2 ESC guideline definitions

Guideline level	Criteria for guideline adherence
Drug types	Treatment with one [*] ACEi [°] or one [*] ARB ⁺ , in combination with one [*] beta-blocker ⁺ and one [*] MRA ⁺ for patients with an LVEF ≤ 35% at Visit 1 Treatment with one [*] ACEi [°] or one [*] ARB ⁺ , in combination with one [*] beta-blocker ⁺ without treatment with an MRA for patients with an LVEF > 35% at Visit 1
Drug type and dose	Guideline adherent with respect to drug types and dosage of all respective guideline drugs ≥ 50% of the recommended target dose [#]

^{*} exactly one

⁺ Only drugs with indication for treatment of HF will be considered as according to guidelines. Any use of a drug from the respective class with no indication for HF leads to treatment classified as non-adherent.

[°] Alternatively: Sacubitril/Valsartan

[#] In case a recommended target dose of a HF medication cannot be defined, the criterion for guideline adherence with respect to drug dose will be considered as fulfilled for this drug (independent from the actual dose)

For identification of the drugs relevant for guideline adherence the following implementations will be used:

- ACEi: ATC texts "ace inhibitors and diuretics", "ace inhibitors, plain"
- ARB: ATC texts "angiotensin ii antagonists and calcium channel blockers", "angiotensin ii antagonists and diuretics", "angiotensin ii antagonists, plain"
- Beta-blocker: ATC texts "alpha and beta blocking agents", "beta blocking agents, non-selective", "beta blocking agents, selective", "beta blocking agents, selective, and thiazides"
- MRA: ATC code C03DA

[Table 4-3](#) describes guideline relevant treatments with indication for HF and provides the respective target doses to be applied for the guideline analyses:

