6.1 Variables with respect to the primary objective

The variables used for the primary analysis are the assessment of the patient's treatment at Baseline (A1) and the assessment of the patient's treatment at Visit 2 (A2) with respect to the adherence to the current ESC guidelines (level 1 and level 2 as described in [section 4.5.1](#)). In addition, the guideline adherence at Visit 3 will be assessed (A3).

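### The SAP's primary analysis drops dose from the adherence definition that the protocol, its sample size and the SAP's own objective use, and the deviations list does not say so

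*SAP*

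**What the plan says.** **Protocol.** Section 2.1 defines adherence as "prescription of all HF specific drugs with level I-A recommendation for a given patient's clinical status at a dose" above 50% of the recommended daily amount. Table 2-1 ties the primary endpoint to that definition: "For definitions of clinically stable patients and adherence to current ESC guidelines see Section 2.1". The sample size section (9.8) applies the same rule to its baseline assumption: "clinical status at a dose of > 50% of the recommended daily dose". Section 9.4.4 adds that "stratified analyses of the primary endpoint will be performed at least for the following subgroups", and refers to the SAP for details.

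**SAP, objective.** Section 3.1 repeats the drug-and-dose definition: "all HF specific drugs with level I-A recommendation for a given patient's clinical status at a dose > 50% of the recommended daily dose".

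**SAP, measures and variables.** Section 4.5.1 says that "two levels of guideline adherence will be used for the analysis". In Table 4-2, level 1 covers drug types and level 2 adds a dose condition. Section 6.1 describes the variables for the primary analysis "with respect to the adherence to the current ESC guidelines (level 1 and level 2 as described in" that section, and does not rank the two levels.

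**SAP, analysis.** Section 7.4.2 does rank them: "The primary analysis will be performed on guideline adherence level 1", with level 2 repeated for sensitivity. Section 7.11 restricts the Visit 2 adherence subgroups to level 1.

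**SAP, deviations.** Section 2.5 undertakes to describe substantial departures from the protocol analysis in detail. Section 7.13 lists three: heart failure medication analysed by visit, the baseline-by-Visit-2 cross table split into separate tables, and less stratification by country. Only the cross-table item concerns the primary analysis, and it comes with an assurance that the content is unaffected.

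**The concern.** The study asks whether referral leads to optimized treatment, and it defines optimized treatment by drug and dose. A class-only primary analysis answers another question. A patient already on every required class at low doses counts as adherent at baseline and so cannot enter the primary denominator, and any later dose increase is invisible to the primary result. A patient who starts the one missing class counts as a success at whatever dose it is given.

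Someone who reads 7.13 to learn what changed would conclude that the primary endpoint is as the protocol set it. The study is single-arm and open, and the SAP already reports the early stop and the last patient visit (23 March 2018) in the past tense. The text available does not show why level 1 was chosen or whether data had been seen by then. That is why a reason and a date matter.

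**Working it through.** **1. Definitions side by side**

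| Place | Dose part of adherence? | Status |
|---|---|---|
| Protocol 2.1; Table 2-1 by reference | Yes, > 50% | Primary objective and endpoint |
| Protocol 9.8, definition | Yes, > 50% | Basis of sample size |
| SAP 3.1 | Yes, > 50% | Primary objective |
| SAP 4.5.1 and 6.1 | Both levels | Not ranked |
| SAP 7.4.2, level 1 | No | Primary analysis |
| SAP 7.4.2, level 2 | Yes, ≥ 50% (Table 4-2) | Sensitivity |
| SAP 7.11, adherence subgroups | No | Level 1 only |

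**2. Direction for the denominator.** By Table 4-2 every level 2 adherent patient is also level 1 adherent. The baseline non-adherent group under level 1 is therefore the same size as under level 2 or smaller, never larger. The numerator changes as well, so the direction of the proportion itself cannot be stated.

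**3. The sample size rests on the dose-based figure.** Protocol 9.8 assumes 20% adherent at baseline by drug and dose, 1,728 patients in the analysis and 2,160 in the prospective period. The protocol does not print the link, but the arithmetic is exact: 2,160 × (1 − 0.20) = 1,728.

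The half-width of a 95% interval at p = 0.25 is 1.96 × √(0.25 × 0.75 / n). With n = 1,728 this is 2.04 points, which agrees with the stated ±2% after rounding. (Exactly ±2.00 would need 1,801 patients; nothing here depends on that gap.)

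**4. Who leaves the denominator (illustration).** Protocol 1.1 cites a Swedish primary care survey with 42% of patients on both a RAAS inhibitor and a beta blocker, and 20% at half the recommended dose or more. Per 100 patients:

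- not adherent by drug and dose: 100 − 20 = 80
- on both classes but under-dosed: 42 − 20 = 22
- share leaving under level 1: 22 / 80 = 27.5%

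The survey has no MRA requirement, while Table 4-2 has one at LVEF ≤ 35%. That can move the share either way. Two assumed examples:

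- 5 of the 20 miss the dose on the MRA: (42 − 15) / (100 − 15) = 27/85 = 31.8%
- only 30 meet the class rules and 15 of them the dose: (30 − 15) / (100 − 15) = 15/85 = 17.6%

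**5. Planned denominator and precision under level 1.** Baseline class-only adherence *a* is not given in the documents, so it is varied. The denominator is 2,160 × (1 − *a*). The 25% is borrowed from the drug-and-dose assumption.

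| *a* (assumed) | Denominator | Half-width at 25% |
|---|---|---|
| 20% | 1,728 | 2.04 points |
| 30% | 1,512 | 2.18 points |
| 42% | 1,253 | 2.40 points |
| 50% | 1,080 | 2.58 points |

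These are planned numbers; SAP 4.2 reports that recruitment stopped early.

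**The case against.** The study is descriptive and exploratory, with no hypothesis test. SAP 7.4.2 reports both levels at every visit and repeats the conditional Visit 2 analysis on level 2, so the drug-and-dose proportion will be available overall. Dose increases also appear in the cardiologist's-advice tables (7.4.3), which 7.11 does run by subgroup. SAP 6.1 and 4.5.1 merely list two levels, and 7.4.2 then ranks them. The precision figures rest on assumptions and move by about half a point at most (2.04 to 2.58).

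Much of this is fair. No data are lost, precision is not the main issue, and the magnitudes are illustrative. Starting a drug counts under level 1 only if it completes the Table 4-2 regimen; a patient missing two classes who starts one stays non-adherent.

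Three things remain. The advice tables pool dose increases with new prescriptions and are not an adherence proportion, so the protocol's endpoint still has no planned subgroup results. SAP 6.1 names level 2 among the variables for the primary analysis, which does not fit its sensitivity role in 7.4.2. And the exploratory clause in SAP 7.12 itself requires modifications to be documented; it does not excuse leaving this one out of 7.13.

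**Conclusion.** The concern holds and needs correction before the results are reported. As written, the proportion labelled primary does not match the objective in the protocol or in the SAP, and the change is not disclosed. That conclusion rests on the text alone. The denominator can only stay the same or shrink. By how much is unknown: about 18% to 32% of the drug-and-dose non-adherent group in the survey-based and assumed examples, which are not bounds. The loss of precision is modest. What is at stake is which proportion is called primary, the missing level 2 subgroups, and the omission from the deviations list.

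Two smaller matters affect level 2 only. Table 4-2 uses ≥ 50% where the objective uses > 50%, and Protocol 9.8 contains both (≥ for the survey figure, > for the definition). A footnote to Table 4-2 also counts the dose condition as met when no target dose can be defined.

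**What to change.** - **Preferred:** in SAP 7.4.2, and for the adherence subgroups in 7.11, make the drug-and-dose classification primary and level 1 supportive. State the same ranking in 4.5.1 and 6.1.
- **If level 1 stays primary:** list it in 7.13 as a change of the primary endpoint, with the reason and the date relative to data access, and show both levels side by side, including in the subgroups.
- **In either case:** reconcile > 50% (Protocol 2.1, the definition in Protocol 9.8, SAP 3.1) with ≥ 50% (SAP Table 4-2, the survey figure in Protocol 9.8) so that one analysis threshold applies. Report how many patients are classified through the undefined-target-dose footnote. Name the level that defines the conform/non-conform strata in SAP 7.1 and 7.6, where none is given.

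**Cost:** SAP wording, table order, a few extra subgroup tables and one count. Every patient is already classified on both levels at every visit, so no new data are needed.

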7.4.3 Cardiologist's advice

The cardiologist's advice will be analysed within the Follow-up Set for all treatments where such an advice has been documented. The following analyses will be performed:

- Analysis on therapy level:
 - Incidence of HF treatment with an advice from the cardiologist will be displayed by preferred name and kind of advice of cardiologist
- Analyses on patient level:
 - Frequencies of cardiologist's advice on patient level will be provided, using the following categories:
 - No change: Cardiologist's advice for at least one HF treatment is "No change", no other advices are given by the cardiologist.

- Treatment intensification: Cardiologist's advice for at least one HF treatment is "Dose increase" or "New prescription" and no advice for "Dose reduction" or "Discontinuation" is given.
- Treatment reduction: Cardiologist's advice for at least one HF treatment is "Dose reduction" or "Discontinuation" and no advice for "Dose increase" or "New prescription" is given.
- Treatment adaption: Cardiologist's advice for at least one HF treatment is "Dose reduction" or "Discontinuation" and for at least one other HF treatment the advice is "Dose increase" or "New prescription".
- Implementation of treatment changes by cardiologist on patient level will be displayed, defined for all patients where the cardiologist's advice on patient level is "Treatment intensification", "Treatment reduction" or "Treatment adaption" as follows:
 - Yes: All recommended HF treatment changes of a patient are implemented by the cardiologist.
 - No: No recommended HF treatment changes of a patient are implemented by the cardiologist.
 - Partially: At least one recommended HF treatment change is implemented by the cardiologist and one other recommended HF treatment change is not implemented by the cardiologist.
- Acceptance of cardiologist's advice on patient level will be provided, defined for all patients where the cardiologist's advice on patient level is "Treatment intensification", "Treatment reduction" or "Treatment adaption" as follows:
 - All changes implemented: acceptance of all cardiologist's change advices
 - No changes implemented: non-acceptance of all cardiologist's change advices
 - Changes partially implemented: acceptance of at least one and non-acceptance of at least one cardiologist's change advice

Reasons for non-acceptance of the cardiologist's advice will be listed by patient and HF treatment.

